#### 8.3.2 Prior/Concomitant Medications/Procedures

Partially missing start/stop dates for prior/concomitant medications and partially missing start dates for prior/concomitant procedures will be imputed in the ADaM dataset for prior/concomitant medications/procedures. For prior/concomitant medications, if the stop date is complete with no missing year, month, or day, and the partially missing start date

Protocol Number: 20200058

Date: 07 February 2023

Page 39 of 67

imputed by the rule below is after the stop date, then the start date will be imputed with the stop date.

Partially missing prior/concomitant medication/procedure start dates will be imputed by the earliest possible date given the non-missing field(s) of the date.

Partially missing prior/concomitant medication stop dates will be imputed with the latest possible date given the non-missing field(s) of the date.

#### 8.3.3 Medical History

Partially missing medical history start dates will be imputed in the ADaM dataset for medical history (for the purposes of calculating durations of PsA and psoriasis). The 16th of the month will be used to impute a partially missing start date that has only the day missing, and July 1st will be used to impute a partially missing start date that has both the month and day missing. If this imputation results in a medical treatment start date is on or after the informed consent date, then the incomplete medical treatment start date will be assigned as one day before earliest recorded informed consent date. If the end date is complete with no missing year, month, or day, and the partially missing start date imputed by the rule above is after the end date, then the start date will be imputed with the end date.

#### 8.4 Detection of Bias

This study has been designed to minimize potential bias by the use of randomization of subjects into treatment groups and the use of blinding. Other factors that may bias the results of the study include:

- Major protocol deviations likely to impact the analysis and interpretation of the efficacy endpoints.
- Subject level unblinding before the primary analysis database lock and formal unblinding.

Important protocol deviations likely to impact the analysis and interpretation of the efficacy endpoints will be tabulated in the Clinical Study Report (CSR).

Any unblinding of individual subjects prior to formal unblinding of the study will be documented in the CSR. The impact of such unblinding on the results observed will be assessed.

Additional sensitivity analyses will be performed to assess the impact of potential biases on the primary endpoint if needed. If any sensitivity analyses are required to evaluate

Protocol Number: 20200058

Date: 07 February 2023

Page 40 of 67

potential biases in the study's conclusions, then the sources of the potential biases and results of the sensitivity analyses will be documented in the CSR.

#### 8.5 Outliers

Extreme data points will be identified during the blinded review of the data prior to primary analysis database lock. Such data points will be reviewed with clinical data management to ensure accuracy. The primary analyses will include outliers in the data. Sensitivity analyses that exclude outliers may be undertaken if extreme outliers for a variable are observed.

#### 8.6 Distributional Characteristics

Distributional assumptions for the primary and secondary endpoints will be assessed If the assumptions are not met, then alternative methods will be utilized. The use of alternative methods will be fully justified in the CSR.

#### 8.7 Validation of Statistical Analyses

Programs will be developed and maintained, and output will be verified in accordance with current risk-based quality control procedures.

Tables, figures, and listings will be produced with validated standard macro programs where standard macros can produce the specified outputs.

The production environment for statistical analyses consists of Amgen-supported versions of statistical analysis software; for example, the SAS System version 9.4 or later.

#### 9. Statistical Methods of Analysis

#### 9.1 General Considerations

#### 9.1.1 Reporting and Analysis Conventions

Summary statistics for continuous variables include sample size (n), mean, standard deviation (SD), median, minimum, the 25th (Q1) and 75th (Q3) percentiles, and maximum. All mean and median values will be formatted to one more decimal place than the measured value. SD values will be formatted to two more decimal places than the measured value. Minimum and maximum values will be presented to the same number of decimal places as the measured value. Frequency summary for categorical variables includes number and percentage. All percentages will be rounded to one decimal place, unless presenting two decimal places is necessary when the percentages are very small. Number and percentage values will be presented as xx (xx.x%). All analysis and summary tables will have the population sample size for each treatment group in the

Protocol Number: 20200058 Date: 07 February 2023

column heading. P-values (2 sided) will be presented with 4 decimal places. All laboratory data will be reported using standard international (SI) units.

Change from baseline will be calculated as (post-baseline minus baseline value).

Percent (%) change from baseline will be calculated as (post-baseline minus baseline value) divided by (baseline value), then multiply by 100. If a baseline value is zero, the percent change from baseline value will be excluded from the summaries.

The analyses involving stratification factors (use of glucocorticosteroid at baseline and use of a csDMARD) will be primarily based on the stratification factors recorded in IWRS at the randomization. Similarly, EE status, as recorded in the IWRS, will be used in all derivations/analyses.

Subject data listings will be provided to support the tables and graphs for selected parameters.

#### 9.1.2 Statistical Methodology for Efficacy

For the Placebo-controlled Phase, treatment outcomes between APR 30 mg BID and placebo will be compared primarily using the FAS. Supportive analysis of the primary endpoint (MDA-joints at Week 16) will use the PP.

For efficacy analyses, data obtained after the day of the first Week 16/Visit 5 dose for subjects who escape early at Week 16/Visit 5 and take at least one dose of IP dispensed at that visit will be excluded from the placebo-controlled summaries through Week 24/Visit 6, unless otherwise specified.

The null and alternative hypotheses for the treatment comparisons can be described as follows:

$$H_0$$
:  $p_{apremilast} = p_{placebo}$  vs.  $H_1$ :  $p_{apremilast} \neq p_{placebo}$ ,

Where p stands for the parameter in comparison, e.g., proportion of subjects achieving MDA-Joints.

Efficacy results will be considered statistically significant after incorporating the strategy for controlling the family-wise Type 1 error rate as described in Section 9.1.3, Multiplicity. All statistical tests will be conducted at the  $\alpha$  = 0.05 (2-sided) level. That is, 2-sided p-values and 2-sided confidence intervals (CIs) for intended point estimates will be reported.

Page 41 of 67

Protocol Number: 20200058

Date: 07 February 2023

Page 42 of 67

Analyses of the long-term data that include the Placebo-Controlled Phase and the Active-treatment Extension Phase will be based on Apremilast Subjects as Randomized population.

#### 9.1.3 Multiplicity

Among statistical tests for the comparisons between the apremilast 30 mg BID and placebo groups, the multiplicity of the analyses performed for the primary and secondary efficacy endpoints will be adjusted using a sequential test procedure to preserve the family-wise type I error rate. The secondary efficacy endpoints and the hierarchical order of the endpoints in the sequential testing will follow those listed in Section 2.1

The sequential test procedure will be conducted as follows:

- Formal statistical tests will be carried out sequentially for selected endpoints, starting with the primary endpoint and then the secondary endpoints by the order same as presented in Section 2.1
- At each step in the sequential testing, statistical significance for a specific endpoint will be claimed only if the p-value for the test is less than 0.05, and the p-values for the tests of all previous endpoints in the hierarchy order are also less than 0.05.
- Once a p-value is 0.05 or greater for the testing of a specific endpoint, only the
  tests for the preceding endpoints will be considered statistically significant; the
  testing for this and the subsequent endpoints will not be considered statistical
  significance and the nominal p-values will be reported.

Of note, the above multiplicity control will only be conducted for the primary endpoint and the secondary endpoints that are evaluated in the Placebo-controlled Phase.

#### 9.2 Subject Accountability

The number of subjects screened, randomized, receiving IP, and completing the study will be summarized.

Subject disposition will be tabulated by treatment arm and study phase. Reasons for discontinuation will be summarized.

The number and percent of subjects randomized will be tabulated by the stratification factors.

Protocol Number: 20200058
Date: 07 February 2023
Page 43 of 67

#### 9.3 Important Protocol Deviations

Important Protocol Deviations (IPDs) categories are defined by the study team before the first subject's initial visit and updated during the IPD reviews throughout the study prior to primary analysis database lock. These definitions of IPD categories, subcategory codes, and descriptions will be used during the course of the study. Eligibility deviations are defined in the protocol.

The protocol deviations/violations will be identified and assessed by clinical research physician or designee throughout all study periods. The protocol deviations/violations for a particular analysis will be defined prior to unblinding of the database. For example, the analysis for the primary endpoint will be based on the 24-week database and definitions of major protocol deviations/violations that may affect the analysis will be determined prior to unblinding of the 24-week database. The protocol deviations/violations will be summarized by treatment arm for the FAS for the double-blind, Placebo-controlled Phase (up through Week 24, regardless of early escape status). Additional summaries will be provided based on Apremilast Subjects as Randomized through Week 52 (Weeks 0-52).

A list of protocol deviations/violations for all subjects will be provided by the Clinical Research Physician and/or through a standardized algorithm prior to the primary analysis database lock and unblinding. Among these protocol deviations, those that may have impact on treatment efficacy will also be determined prior to the primary analysis database lock and used to identify which subjects are to be removed from the Per Protocol Set . These protocol deviation data will be integrated into the clinical database.

Additionally, protocol deviations and important protocol deviations related to COVID-19 will be summarized.

#### 9.4 Demographic and Baseline Characteristics

Demographics and baseline characteristics will be summarized descriptively by treatment group using the FAS. In addition, demographics and baseline disease characteristics will also be summarized for subjects who escape early, subjects who do not escape early and subjects who discontinue early. The comparability of the treatment groups for each relevant characteristic will be assessed descriptively in table format; no statistical hypothesis tests will be performed on these characteristics.

Protocol Number: 20200058 Date: 07 February 2023

#### 9.4.1 Demographics

Demographic characteristics including age, sex, race, ethnicity, geographic region, weight (kg) and height (cm), etc. (please refer to CRF for available variables) will be summarized.

Continuous variables will be summarized using descriptive statistics (n, mean, standard deviation, median, minimum, and maximum, etc.). Categorical variables will be summarized with counts and percentages.

Summary statistics will be provided by treatment group for the following continuous variables:

- Age (years)
- Weight (kg)
- Height (cm)

Number and percentage will be provided by treatment group for the following categorical variables where sufficient numbers allow:

- Age category (< 65, ≥ 65 years; < 40, ≥ 40 to < 65, ≥ 65 to < 75, ≥ 75 to < 85, ≥

   85 years, if appropriate)
- Sex (male, female)
- Race (American Indian or Alaska Native, Asian, Black or African American,
   Native Hawaiian or Other Pacific Islanders, White, Not Collected or Unknown)
- Ethnicity (Hispanic or Latino, Not Hispanic or Latino, Not Reported, Unknown)
- Region (North America, Europe, Rest of the World [including Russia])
- Weight category (< 70,  $\geq$  70 to < 85,  $\geq$  85 to < 100,  $\geq$  100 kg)

•

Most variables will be used as recorded on the CRF.

The demographics summary will include the frequencies of alcohol history (current user, past user, never used), and smoking status (current user, past user, never used).

#### 9.4.2 Baseline or Disease Characteristics

Summary statistics will be provided by treatment group for all relevant baseline characteristics continuous variables, such as the following:

Page 44 of 67

Protocol Number: 20200058 Date: 07 February 2023

Page 45 of 67

- Duration of PsA (from the date of diagnosis to the date of informed consent; months)
- Baseline prednisone (or equivalent) dose (mg/day)
- Concomitant Methotrexate dose (mg/week)
- Concomitant Sulfasalazine does (g/day)
- cDAPSA
- Swollen joint count (66 joints)
- Tender joint count (68 joints)
- Patient's global assessment of disease activity (0 to 100 mm VAS)
- Patient's assessment of pain (0 to 100 mm VAS)
- PsAID-12
- HAQ-DI score and categories
- Physician's global assessment of disease activity (0 to 100 mm VAS)
- LEI in subjects with pre-existing enthesopathy

- PASDAS
- Psoriasis BSA

Protocol Number: 20200058 Date: 07 February 2023

Page 46 of 67

hsCRP (mg/L)

Number and percentage will be provided by treatment group for all relevant categorical variables, such as the following (subcategories under a specific category of a variable, where applicable):

- Baseline glucocorticosteroid use (yes, no) in IWRS and in actual data, if different
- Prior/concomitant use of a csDMARD, either MTX or SSZ, (csDMARD-naïve; csDMARD use prior to baseline; or csDMARD use prior to and concomitant at baseline) in IWRS and in actual data, if different
- Prior use csDMARD (yes, no)
- Concomitant use of csDMARD (yes, no)
- Tender joint count (2, 3, 4)
- Swollen joint count (2, 3, 4)
- Swollen or tender joint count (2, 3, 4, 5, 6, 7, 8)
- Swollen and tender joint count (0, 1, 2, 3, 4)
- cDAPSA (≤ 4 for remission, > 4 and ≤ 13 for low disease activity, > 13 and ≤ 27 for moderate disease activity, and > 27 for high disease activity)
- Patient's global assessment of disease activity VAS (≤20, >20)
- Patient's assessment of pain VAS (≤15, >15)
- PsAID-12 (≤ 4, > 4)
- PASDAS (≤3.2, >3.2 to < 5.4, ≥ 5.4)

- HAQ-DI (≤0.5, > 0.5)
- LEI (= 0, > 0)
- LEI (≤1, >1)
- Psoriasis BSA (≤3%, >3%)

Protocol Number: 20200058

Date: 07 February 2023

Page 47 of 67

#### 9.4.3 Medical History

Medical history will be coded according to the Medical Dictionary for Regulatory Activities (MedDRA, version 25.1 or later). A frequency summary (number and percentage) of medical history will be presented by treatment group, system organ class (SOC), and preferred term (PT).

#### 9.4.4 Prior and Concomitant Procedures

The prior and concomitant procedures will be coded using the MedDRA, version 25.1 or higher. Frequency summaries of prior procedures for Full Analysis Set, and concomitant procedures for Safety Analysis Set will be provided by treatment group, SOC and PT.

Prior procedures are defined as procedures or surgeries that were started before the first dose of IP (regardless of they ended before the first dose of IP). Prior procedures that continue or occur after the first dose of IP will also be reported as concomitant procedures.

Concomitant procedures will be similarly analyzed as concomitant medications in the next section.

#### 9.4.5 Prior and Concomitant Medications

The Anatomical Therapeutical Chemical (ATC) coding scheme of the World Health Organization Drug Dictionary (WHODD version March 2020 or later) will be used to group medications into relevant categories. Frequency summaries of prior medications for Full Analysis Set and concomitant medications for Safety Analysis Set will be provided by treatment group, ATC2 level, and standardized medication name.

Prior medications are defined as those started before the first dose of IP (whether or not ended before the first dose of IP). Prior medications that continue after the first dose of IP will be also reported as concomitant medications.

Protocol Number: 20200058

Date: 07 February 2023

Page 48 of 67

Concomitant medications and procedures will be summarized differently for each phase/period of the study. The concomitant medication for the Placebo-controlled Phase will be summarized by treatment group using the Safety Analysis Set. The concomitant medication for the Apremilast-exposure Period will be summarized by a total group only of those who were treated with apremilast (irrespective of when the apremilast exposure starts [at Week 0, 16, or 24]). In addition, to account for possible resumption/initiation of non-study medications treating PsA during the Observational Follow-up Phase, concomitant medications will be summarized for the Observational Follow-up Phase based on all subjects who entered the phase.

A concomitant medication for the Placebo-controlled Phase is defined as a non-study medication that meets either one of the following 2 criteria:

- 1. Is started on or after the date of the first dose of IP, and
  - before the date of the first Week 16/Visit 5 dose for placebo-treated subjects who escape early at Week 16/Visit 5 and take at least one dose of IP dispensed at that visit, or
  - before the date of the first Week 24/Visit 6dose for subjects who complete
     Week 24/Visit 6 dose, except for placebo-treated subjects who escape early,
     or
  - on or before the date of the last study visit (including the Early Termination Visit and excluding any unscheduled visits associated with the Early Termination Visit and the Observational Follow-up Visit) for all other subjects (i.e., subjects who discontinue prior to Week 24/Visit 6, with the exception of placebo-treated subjects who discontinue after early escape and have taken at least one dose of IP dispensed at Week 16/Visit 6).
- 2. Is started before the date of the first dose of IP, and stopped on or after the date of the first dose of IP, or recorded as ongoing.

A concomitant medication for the Apremilast-exposure Period is defined as a non-study medication that meets either one of the following 2 criteria:

is started on or after the date of the first dose of apremilast after being randomized (at Week 0/Visit 2) or escaped/transitioned (at Week 16/Visit 5 or Week 24/Visit 6) to apremilast dose group and stopped on or before the date of the last study visit (including the Early Termination Visit and excluding any unscheduled

Protocol Number: 20200058 Date: 07 February 2023

visits associated with the Week 48/Visit 9 and the Early Termination Visit, and the Observational Follow-up Visit) for subjects who have completed the study or have discontinued early, or on or before the data cutoff date for ongoing subjects.

2. is started before the date of the first dose of apremilast after being randomized or escaped/transitioned to apremilast dose, and stopped on or after the date of the first dose of apremilast, or recorded as ongoing.

A concomitant medication for the Observational Follow-up Phase is defined as a nonstudy medication that meets either one of the following 2 criteria:

- 1. is started after the date of the Week 48/Visit 9 (for subjects who have completed the study) or the Early Termination Visit (for subjects who have discontinued early), but no later than 28 days after the last dose of IP in the study.
- 2. is started on or before the date of the Week 48/Visit 9 (for subjects who have completed the study) or the Early Termination Visit (for subjects who have discontinued early), and stopped after this date, or recorded as ongoing.

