8.1. Permitted Concomitant Medications and Procedures

The following concomitant medications and procedures are permitted during the study:

- Oral glucocorticosteroids are to be taken on a stable dose up to the Week 24 Visit:
 - Prednisone ≤ 10 mg/day (or prednisolone equivalent) for at least 4 weeks prior to the Baseline Visit must be continued and maintained through the Week 24 Visit (change in dose and/or discontinuation are not allowed except for safety reasons or for lack of availability).
- NSAIDs (and/or narcotic analgesics) are allowed during the study, provided that the NSAIDs are taken on a stable dose for at least 2 weeks prior to the Baseline Visit.
 - The stable dose of NSAIDs or narcotic analgesics must be continued and maintained from the Baseline Visit through the Week 24 Visit. Change in doses, increase or decrease, and/or discontinuation of NSAIDs or narcotic analgesics will not be allowed except for safety reasons or for lack of availability. After the Week 24 Visit, the dose of NSAIDs or narcotic analgesics may be adjusted as clinically required.
 - NSAIDs or narcotic analgesics that are administered on an as needed basis (PRN) should be recorded on the Prior/Concomitant Medications page of the eCRF.

• csDMARDs –

- Only 1 csDMARD (MTX or SSZ) for the treatment of PsA is permitted during the first 24 weeks of the study, provided that the treatment is taken on a stable dose ≥ 3 months prior to the Baseline Visit.
- Subjects exposed to MTX or SSZ and stopped treatment due to intolerance or due to safety reasons may enter the study provided that treatment was stopped within at least 4 days of the Baseline Visit
 - The allowed dose for permitted csDMARDs are: MTX (oral or parenteral) ≤ 25 mg/week; SSZ (oral) ≤ 3 gm/daily
- Low-dose aspirin (acetylsalicylic acid, up to 325 mg per day) for cardiovascular prophylaxis.
- Loperamide and antidiarrheal drugs with antisecretory effect (eg, racecadotril).

Protocol CC-10004-PSA-013

• A nonmedicated skin emollient (eg, Eucerin® cream) for body psoriasis lesions only.

After the Week 24 Visit, changes in the following therapy will be permitted as clinically required for subjects with worsening arthritic symptoms of PsA:

- Change of NSAID type and/or dose
- Parenteral glucocorticoids are allowed, provided that the following criteria are met:

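### SAP 9.4.5: the Apremilast-exposure concomitant-medication table omits a drug newly started on apremilast that continues past the last visit, so it understates continuing added therapy

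*SAP*

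**What the plan says.** SAP 9.4.5 gives a separate two-criterion definition of a concomitant medication for each phase or period. A drug needs to meet only one of the two.

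**Apremilast-exposure Period.** Criterion 1 takes drugs begun on or after the first apremilast dose and adds a stop condition: "to apremilast dose group and stopped on or before the date of the last study visit". The last visit here may be the Early Termination Visit but not the Observational Follow-up Visit. For subjects still in the study the limit is "or on or before the data cutoff date for ongoing subjects". Criterion 2 takes a drug that "is started before the date of the first dose of apremilast after being randomized or escaped/transitioned to apremilast dose". Its stop condition, unlike that of criterion 1, makes room for continuing drugs: "and stopped on or after the date of the first dose of apremilast, or recorded as ongoing".

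**Placebo-controlled Phase.** Criterion 1 opens with "Is started on or after the date of the first dose of IP, and" and then sets upper limits on that same start date, for example "before the date of the first Week 16/Visit 5 dose for placebo-treated subjects who escape early". It has no stop condition.

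**Observational Follow-up Phase.** Criterion 2 takes drugs begun on or before Week 48 or Early Termination "and stopped after this date, or recorded as ongoing". This summary is based on subjects who entered the phase.

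Three other places bear on the point. SAP 8.3.2 imputes stop dates only when they are partially missing. Protocol 9.9.2 plans frequency tables of all concomitant treatments documented in the study. Protocol 8.1 states: "After the Week 24 Visit, changes in the following therapy will be permitted as clinically required for subjects with worsening arthritic symptoms". The therapies it lists include NSAIDs, glucocorticoids and non-biologic DMARDs.

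**The concern.** In criterion 1 a stop date on or before the last visit is a condition of being counted. A drug begun on apremilast and still being taken has no stop date, so it fails. Criterion 2 cannot pick it up, because that criterion requires a start before apremilast.

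The omission is selective. A course that begins and ends on apremilast is counted; a continuing drug begun the same day is not. Efficacy beyond Week 24 is uncontrolled and summarized descriptively (Protocol 9.6.5), and background therapy may change from that point. A reader of the long-term results will want to know how much therapy was added, and this table would err in one direction, towards too little.

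**Working it through.** No figure in the plan depends on this rule, so there is none to reproduce. The check applies the definitions to illustrative drug records.

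**Inputs.** Study days are the target days in SAP Appendix A, Table 5: Week 24 is day 169 and Week 48 is day 337. Let F be the day of the first apremilast dose (1 in the apremilast arm; 169 for a placebo subject transitioned at Week 24), L = 337 the last counted visit, s the start day and e the stop day (none if ongoing).

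**Rules.**
- Apremilast-exposure as written: (s ≥ F and e exists and e ≤ L) or (s < F and (e ≥ F or ongoing)).
- Apremilast-exposure with a start-date bound: (F ≤ s ≤ L) or (s < F and (e ≥ F or ongoing)).
- Placebo-controlled: (1 ≤ s < 169) or (s < 1 and (e ≥ 1 or ongoing)).
- Follow-up, criterion 2: s ≤ L and (e > L or ongoing).

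**Two records worked through, apremilast arm.** For s = 200 and e = 300: 200 ≥ 1 and 300 ≤ 337, so it is counted. For s = 200 and ongoing: criterion 1 fails because there is no e, and criterion 2 fails because 200 is not below 1. It is not counted.

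**All records.**

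| Subject | Start, stop (day) | As written | Start-date bound | Placebo-controlled | Follow-up |
|---|---|---|---|---|---|
| Apremilast arm | −90, ongoing | yes | yes | yes | yes |
| Apremilast arm | 60, 90 | yes | yes | yes | no |
| Apremilast arm | 60, ongoing | **no** | yes | yes | yes |
| Apremilast arm | 200, 300 | yes | yes | no | no |
| Apremilast arm | 200, 350 | **no** | yes | no | yes |
| Apremilast arm | 200, ongoing | **no** | yes | no | yes |
| Placebo, moved at Week 24 | −90, ongoing | yes | yes | yes | yes |
| Placebo, moved at Week 24 | 60, 90 | no | no | yes | no |
| Placebo, moved at Week 24 | 60, ongoing | yes | yes | yes | yes |
| Placebo, moved at Week 24 | 200, 300 | yes | yes | no | no |
| Placebo, moved at Week 24 | 200, 350 | **no** | yes | no | yes |
| Placebo, moved at Week 24 | 200, ongoing | **no** | yes | no | yes |

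The five bold entries are drugs taken during apremilast exposure but missing from its table. Bounding the start date recovers all five. It still excludes the one record that ended before apremilast began (placebo subject, days 60 to 90), which is correct.

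**Could the text be read otherwise?** If the allowance for ongoing drugs in criterion 2 were a free-standing route, the ongoing records would be counted. The reading is strained: the phrase completes the stop condition of a criterion limited to earlier starts, and the SAP announces two criteria, not three. Even then, the day 200 to 350 record is lost in both groups. In criterion 1 the word *ongoing* describes subjects, not drugs. SAP 8.3.2 gives an ongoing drug no stop date.

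**The case against.** The strongest reply is that little is lost from the report as a whole.

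- The Follow-up definition takes in drugs begun by Week 48 or Early Termination that continue beyond it, and completers and early discontinuers are all planned to enter that phase. Drugs begun before the first Week 24 dose in the apremilast arm are also in the Placebo-controlled summary.
- The tables count subjects by ATC2 level and standardized medication name. A subject already taking methotrexate, prednisone or an NSAID at the first apremilast dose is counted through criterion 2, and a later dose change adds nothing to such a table.
- Injections and short oral steroid courses normally end, and are counted unless they end after the last visit.
- No endpoint, test or imputation rule visible in the documents uses this classification.

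All of this stands, and it limits the point. A reader might infer that every drug begun on apremilast and still in use disappears from the report, or that changes of dose in background therapy go uncounted. The documents support neither.

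What the reply does not remove is the gap in the table itself. The Follow-up summary is meant to show therapy resumed or begun after treatment. It does not separate drugs begun during apremilast exposure, and it covers only subjects who entered that phase. For a drug begun after Week 24 and still ongoing, it is the only summary left. The Placebo-controlled summary stops at Week 24.

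**Conclusion.** The point holds as a minor drafting error. As written, criterion 1 leaves out of the Apremilast-exposure table any newly started drug that is ongoing at the last visit or ends during follow-up, and the error runs towards understating continuing added therapy. The contrast with the Placebo-controlled definition suggests that *stopped* was written where *started* was meant. The result also falls short of the complete tabulation that Protocol 9.9.2 describes.

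The size cannot be given. The documents report no rate of new starts on apremilast and no share of these still ongoing at the end. A reader might suppose that most new starts are lost; nothing in the documents supports that or any other proportion. The records above illustrate the logic and are not estimates.

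The conclusion rests on reading the two criteria literally and on ongoing drugs having no stop date in the data. It concerns a descriptive table only. The Week 16 primary analysis, alpha and power are unaffected.

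**What to change.** In criterion 1 of the Apremilast-exposure definition in SAP 9.4.5, change *stopped* to *started*, so that the upper limit applies to the start date. Apply the same limit to the data cutoff date for subjects still in the study. Leave criterion 2 unchanged. The rule then matches the Placebo-controlled Phase definition.

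SAP 9.4.4 says concomitant procedures are analyzed similarly, so confirm that the corrected condition is used there too.

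The cost is one word in the SAP and one condition in the program. No new data are needed.
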